2.1 Procedures

2.1.1 Recruitment and Enrollment

Participant recruitment will be conducted over a one-year period using a comprehensive outreach strategy encompassing both online and offline channels to reach young men who have sex with men (YMSM) in two study locations: Ubon Ratchathani and Mahasarakham. The initial target sample size will be 600 participants (300 per province).

Offline recruitment will involve the distribution of QR codes linking to an online screening form. These will be disseminated at public venues and community gathering points frequented by the target population, including local markets, university canteens, schools (through educational sessions on military conscription), shopping centers, and entertainment venues. The research team will also organize community engagement events such as volleyball tournaments, photography contests, and cultural festivals (e.g., Mor Lum folk music events), as well as outreach activities at bars and clubs popular among YMSM. Collaboration with university lecturers, local public health agencies, and public hospitals will support recruitment efforts.

Online recruitment will be conducted through targeted communication campaigns on social media platforms, supplemented by peer-driven outreach activities to increase engagement and visibility among potential participants.

Interested individuals will be required to complete an online eligibility screening form. Those who meet the eligibility criteria will receive detailed study information and complete an initial electronic consent process. A study team member will then follow up to schedule an appointment, during which a comprehensive informed consent discussion will be conducted. Written informed consent and a photocopy of the participant's national identification card will be obtained. Participants will then view a demonstration video on how to self-collect rectal swab specimens, complete the baseline questionnaire, and provide their first set of biological specimens.

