2.1.2 Data Collection

Data will be collected at five time points: baseline, and months 6, 12, 18, and 24 of follow-up. At each round, participants will complete self-administered surveys using tablets or smartphones via the Qualtrics platform. A Unique Identification Code (UIC) will be used to longitudinally link participant data across time points. The UIC will consist of the first letter of the province name, followed by an underscore, the first two letters of the participant's last name, and the date of birth in the DDMMYYYY format (e.g., P_AB01012025). To minimize entry errors, local research staff will select the UIC from a predefined list using a forced-choice format.

At each follow-up round, participants will self-collect biological specimens, including urine samples and rectal swabs, for chlamydia and gonorrhea testing. All specimens will be transported under temperature-controlled conditions to the Office of Disease Prevention and Control 10 (ODPC 10) in Ubon Ratchathani for laboratory analysis. Prior to specimen collection, participants will watch a standardized instructional video to ensure correct self-collection procedures.

HIV-related clinical data including the date of the most recent HIV test, HIV status, initiation of antiretroviral therapy (ART), treatment continuity, and viral load results will be extracted from the national HIV database maintained by the Ministry of Public Health using the participant's national identification number. Access to this database will be restricted to the principal investigator and the study statistician to ensure data confidentiality. All data will be stored in encrypted and password-protected formats on secure institutional servers.

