3.2 Secondary Objectives

- To evaluate the effect of the intervention on reducing HIV incidence.
- To evaluate the effect of the intervention on reducing the incidence of chlamydia trachomatis and gonorrhea infections.
- To evaluate the effect of the intervention on reducing sexual risk behaviors (e.g., condomless anal intercourse).
- To evaluate linkage to and retention in HIV care among HIV-positive participants, including the proportion with undetectable viral load.
- To evaluate the uptake of pre-exposure prophylaxis (PrEP) among HIV-negative participants.

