3.4 Secondary Outcomes

- **HIV incidence:**

Number of new HIV infections per 100 person-years, based on seroconversion during follow-up, using data from the Ministry of Public Health national HIV database.

- **Incidence of Chlamydia and Gonorrhea infections:**

Number of new chlamydia and gonorrhea infections identified at each follow-up round, based on self-collected urine and anal specimens.

- **Sexual risk behavior:**

Proportion of participants reporting condomless anal intercourse with male partners in the past 6 months, measured via self-reported survey data.

- **Retention in HIV care:**

Proportion of HIV-positive participants who remain engaged in HIV care at months 6, 12, 18, and 24, based on data from the Ministry of Public Health national database.

- **Undetectable viral load:**

Proportion of HIV-positive participants with a viral load of <200 copies/mL at each follow-up round, as reported in the Ministry of Public Health national database.

- **Current PrEP use:**

Proportion of HIV-negative participants who report currently using PrEP at each follow-up round, based on self-reported data.

4. Analysis Populations

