4.1 Intention-to-Treat (ITT) Population

The ITT population will include all participants who completed the baseline assessment and were assigned to either the intervention or control site, regardless of their level of

participation in the intervention activities thereafter. This population will serve as the primary analytic population for evaluating the effectiveness of the intervention, reflecting real-world implementation outcomes.

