6.2 Primary and Secondary Outcome Analyses

To evaluate the effects of the intervention over time, Generalized Estimating Equations (GEE) with appropriate link functions (e.g., logit for binary outcomes, identity for continuous outcomes) will be used.⁸ The models will include study arm (intervention vs. control), time (follow-up visits), and their interaction term to estimate intervention effects over time. Robust standard errors will be used to account for within-subject correlation. Person-time will be calculated and compared using rate ratios and 95% confidence intervals.

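### PrEP uptake is a secondary objective, but the only PrEP outcome is current use at six-monthly rounds, and no outcome identifies men who newly start

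*Combined protocol and SAP*

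**What the plan says.** - **Objective (SAP 3.2):** "To evaluate the uptake of pre-exposure prophylaxis (PrEP) among HIV-negative participants".
- **Outcome (SAP 3.4):** "Proportion of HIV-negative participants who report currently using PrEP at each follow-up round, based on self-reported data". The word *currently* is not defined. No outcome covers new starts, ever use or use since the last visit.
- **Spacing (Protocol 2.1.2):** "Data will be collected at five time points: baseline, and months 6, 12, 18, and 24 of follow-up".
- **A neighbouring outcome with a look-back (SAP 3.4):** "Proportion of participants reporting condomless anal intercourse with male partners in the past 6 months". This window spans the gap between rounds; the PrEP outcome has none.
- **Population (SAP 4.1):** "all participants who completed the baseline assessment and were assigned to either the intervention or control site". Neither this definition nor the eligibility criteria (Protocol 2.2) sets apart men already on PrEP.
- **Registry extract (Protocol 2.1.2):** besides the latest test date and HIV status, "initiation of antiretroviral therapy (ART), treatment continuity, and viral load results will be extracted from the national HIV database". PrEP is not listed.
- **Model (SAP 6.2):** "The models will include study arm (intervention vs. control), time (follow-up visits), and their interaction term to estimate intervention effects over time". Baseline is not said to be a level of time.

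**The concern.** Uptake ordinarily means starting, and the SAP uses the word that way elsewhere. SAP 3.1 ties testing uptake to men never tested before, and SAP 3.3 counts testing cumulatively over 24 months. The PrEP outcome is restricted to neither new users nor a cumulative count.

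Current use differs from uptake in two ways. A man who starts after one round and stops before the next is never counted. A man who was on PrEP before enrolment and continues is counted at every round without having started during the study. The first loses part of any effect on starting. The second dilutes the comparison or, if the two cities differ at baseline, distorts it. At stake is whether a named secondary objective gets a clear answer.

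**Working it through.** The plan states no PrEP figure to reproduce. Its sample size (300 per province, Protocol 2.1.1) comes with no alpha, power or effect size, so that cannot be reproduced either. The checks below are illustrative.

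**Inputs.** From the documents: 6-month spacing, 24 months, 300 per site, and retention above 60% per round (SAP 2), so 0.60 × 300 = 180 per site at the floor. Assumed: two-sided alpha 0.05; cumulative new starts C over 24 months of 20% (control) and 35% (intervention); exponential time on PrEP with mean m months; everyone HIV-negative. Having only one city per arm is ignored, so the powers serve only to compare outcomes with each other.

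**1. Episodes that fall between rounds.** With starts spread evenly over the interval, the share ended by the next round is 1 − (m/6)(1 − e^(−6/m)).
- m = 3: 1 − 0.432 = 57%
- m = 6: 1 − 0.632 = 37%
- m = 12: 1 − 0.787 = 21%
- m = 24: 1 − 0.885 = 12%

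**2. Equal persistence, no baseline users.** The monthly start rate is λ = −ln(1 − C)/24, which gives 0.0093 and 0.0179; the stop rate is μ = 1/m. Current use at month 24 is [λ/(λ+μ)] × (1 − e^(−24(λ+μ))). Power is Φ[(d − 1.96·√(2p̄(1−p̄)/n)) / √((p₁(1−p₁)+p₂(1−p₂))/n)].

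For fully captured initiation, 20% versus 35% at n = 300: (0.15 − 1.96 × 0.0365)/0.0359 = 2.19, so power is 98.6%. At n = 180 it is 89.3%.

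| Mean months on PrEP | Current use, month 24 | Power, 300/site | Power, 180/site |
|---|---|---|---|
| 3 | 2.7% vs 5.1% | 33% | 22% |
| 6 | 5.2% vs 9.6% | 54% | 36% |
| 12 | 9.0% vs 16.2% | 76% | 54% |
| 24 | 12.9% vs 22.9% | 89% | 70% |

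The 15-point difference in starts becomes 2.4 to 10.0 points. The ratio is not lost: 5.1/2.7 = 1.9 at 3 months, against 35/20 = 1.75 for starts. The loss is in absolute difference and precision.

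**3. Unequal persistence.** Take one interval with 30% versus 20% starting.
- Mean 3 months at both sites: 0.30 × 0.432 = 13.0% versus 0.20 × 0.432 = 8.6%, so the ratio of 1.5 is kept.
- Mean 3 months (intervention) against 9 (control): 13.0% versus 0.20 × 0.730 = 14.6%, so the order reverses.

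In the 24-month model with 10% already on PrEP at each site, both sites read 10.0% when mean durations are 12 months (control) and 6.2 months (intervention).

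**4. Use before enrolment.** Let p₀ be on PrEP at baseline and continue, and let 10% versus 20% of the rest be new users. Follow-up use is p₀ + (1 − p₀) × 0.10 versus p₀ + (1 − p₀) × 0.20.
- p₀ = 0: ratio 2.00, power 93% at 300 per site
- p₀ = 10%: 19% vs 28%, ratio 1.47, power 74%
- p₀ = 20%: 28% vs 36%, ratio 1.29, power 56%
- p₀ = 30%: 37% vs 44%, ratio 1.19, power 42%

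With baseline use of 20% (control) and 10% (intervention), both sites read 28%: 0.20 + 0.80 × 0.10 and 0.10 + 0.90 × 0.20. The changes from baseline are 8 and 18 points, so a comparison of changes still shows the 10-point difference.

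**5. Initiation without a new survey item.** If uptake is the first report of current use at any of four attended rounds, the proportion seen is 1 − (1 − q)⁴, with q = [λ/(λ+μ)] × (1 − e^(−6(λ+μ))). This gives 9.1% vs 16.8% (m = 3), 13.1% vs 23.6% (m = 6) and 16.1% vs 28.6% (m = 12). It still misses short episodes, but the difference is larger than for month-24 current use in each case.

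**The case against.** **The planned model already deals with baseline use.** This largely stands if baseline is a level of time, because the arm-by-time term then compares changes. A reader might infer that a standing difference between the cities, say 15% versus 5% at every round with nobody starting or stopping, would be reported as uptake. The documents do not support that. The odds ratio, (0.15/0.85)/(0.05/0.95) = 3.35, would sit in the arm term, and the interaction would be zero. What remains is that SAP 6.2 and Protocol 2.4.2 describe time as follow-up visits or rounds. If baseline is left out, an effect present by month 6 falls into the arm term together with any pre-enrolment difference. No model term recovers episodes that fall between rounds.

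**The objective does not say that the intervention must raise new starts, and the questionnaire is not in the documents.** Both are true. Reading uptake as starting rests on ordinary meaning and on SAP 3.1 and 3.3. An item on current use may carry a look-back that the SAP does not state, so measurement strictly on the survey day should not be assumed.

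**A false null depends on chosen inputs.** It does. The one-interval reversal needs intervention-site users to stay on PrEP a third as long. The documents give no persistence figures and no reason to expect such a gap.

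**Current use is a legitimate measure.** It is a sensible measure of coverage and belongs in the plan. PrEP is also absent from Protocol 1.4 and from the aims in SAP 1.2, which limits the weight of the point.

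**Conclusion.** The mismatch is in the text: the objective is uptake, the only outcome is prevalence of current use, and nothing listed identifies new users. With equal persistence the consequence is a smaller absolute difference and lower power: 33% to 89% for month-24 current use, against 98.6% for fully captured initiation, at 300 per site with assumed starts of 20% versus 35% and mean durations of 3 to 24 months. Those inputs are assumptions, and the 98.6% supposes that every start is recorded.

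A reader might go further and infer that the objective cannot be answered, or that a real rise would show as no effect. The documents do not support either as a general statement. Current use still carries information about uptake, and a null or reversed result needs shorter persistence at the intervention site or a baseline imbalance. The latter is largely removed if baseline is a level of time, which the SAP does not say. The point concerns one of six secondary outcomes and leaves the primary result unaffected; its severity is minor to moderate.

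**What to change.** 1. Add to SAP 3.4: *PrEP initiation: among participants HIV-negative and not using PrEP at baseline, first report of PrEP use by month 24.* Link it to the uptake objective in SAP 3.2.
2. Analyse it as time to first report by round (a discrete-time model), or with missed rounds imputed under SAP 5.1. Expected retention is only above 60% per round, and a simple any-round proportion gives men who attend more often more chances to be counted, so unequal attendance could look like unequal uptake. State how a first report after a missed round is dated.
3. Keep current PrEP use as a separate coverage outcome, define *currently*, and make baseline a level of time in its GEE.
4. Confirm that the baseline survey asks about PrEP. The documents do not say so, and the new denominator depends on it.
5. If the survey can still be changed, add one item on any PrEP use since the last visit. If it cannot, state that episodes falling wholly between rounds are missed; the new outcome does not cure that by itself.

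Cost: mainly SAP wording, plus one optional survey question. Baseline users leave the initiation denominator, and one more secondary outcome enters any adjustment under SAP 6.3.

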4.1 Intention-to-Treat (ITT) Population

The ITT population will include all participants who completed the baseline assessment and were assigned to either the intervention or control site, regardless of their level of

participation in the intervention activities thereafter. This population will serve as the primary analytic population for evaluating the effectiveness of the intervention, reflecting real-world implementation outcomes.

4.2 High Exposure Subgroup

This subgroup will include participants from the intervention site who reported a high level of engagement with the BAAN HUG-M intervention activities at each follow-up round. This subgroup will be analyzed separately to evaluate the impact of sustained and intensive participation on health behaviors and outcomes.

5. Data Management and Quality Assurance

5.1 Handling of Missing Data

Data collection will be conducted using an online survey platform (Qualtrics)⁴ with enforced “force response” and appropriately programmed skip logic to minimize item non-response and ensure completeness of key variables. These design features significantly reduced the risk of missing data, especially at baseline.

However, due to the longitudinal nature of the study and the possibility of participant drop-out or missed follow-up visits, some missing data may still occur, particularly in follow-up rounds. In such cases, missing values will be clearly identified and coded within the dataset.

For statistical analysis, appropriate methods will be employed to handle missing data. When the proportion of missing data is non-trivial, we will compare the characteristics of participants with complete versus incomplete data. Depending on the nature and extent of missingness, we will use multiple imputation (MI) or maximum likelihood (ML) methods under the assumption that the data are missing at random (MAR).⁵ Sensitivity analyses using pattern-mixture models will also be conducted to assess the robustness of the MAR assumption.⁶ Complete case analysis may be applied in cases where missingness is minimal and ignorable.

5.2 Data Cleaning and Preparation

Following data export from the Qualtrics platform, the research team will perform systematic data cleaning procedures to ensure data quality, consistency, and readiness for analysis. This process will be conducted using STATA⁷ syntax and command scripts to automate checks and corrections.

Key steps in data cleaning will include the detection of outliers and logically inconsistent responses, verification of skip logic compliance, and range checks for numeric variables. Variables that are expected to align conditionally (e.g., responses to dependent questions) will be cross validated for logical coherence.

In preparation for analysis, data from three key sources will be merged and harmonized:

- Self-administered questionnaires (Qualtrics)
- Laboratory-based test results (chlamydia and gonorrhea from self-collected urine and anal specimens)

- HIV-related clinical data (e.g., HIV status, ART access, viral load) from the Ministry of Public Health national HIV database.

To enable accurate data linkage across timepoints and data sources, participants will be assigned a Unique Identification Code (UIC), which comprises parts of the participant's last name and date of birth. Additionally, linkage to the Ministry of Public Health national HIV database will use the participant's 13-digit national ID number alongside the UIC to ensure robust data matching. The UIC will play a central role in aligning participant records across survey rounds, lab results, and national HIV data systems while preserving confidentiality.

5.3 Variable Coding and Labeling

All variables will be coded and labeled systematically following a standardized data dictionary. Coding will be consistent across all follow-up rounds. For example, dichotomous variables will be labeled as "1 = Yes" and "0 = No," and Likert-scale items will include clearly defined scales. This consistency supports accurate interpretation, longitudinal comparison, and reproducibility of analyses in the future.

6. Statistical Methods

6.1 Descriptive Analysis

Descriptive statistics will be used to summarize baseline characteristics and study variables, stratified by study arm (intervention vs. control). All statistical comparisons will be made between the two study sites — Ubon Ratchathani (intervention site) and Mahasarakham (control site) to assess the impact of the BAAN HUG-M intervention over time. Frequencies and percentages will be used for categorical variables and means with standard deviations or medians with interquartile ranges will be used for continuous variables, depending on their distribution.

6.2 Primary and Secondary Outcome Analyses

To evaluate the effects of the intervention over time, Generalized Estimating Equations (GEE) with appropriate link functions (e.g., logit for binary outcomes, identity for continuous outcomes) will be used.⁸ The models will include study arm (intervention vs. control), time (follow-up visits), and their interaction term to estimate intervention effects over time. Robust standard errors will be used to account for within-subject correlation. Person-time will be calculated and compared using rate ratios and 95% confidence intervals.

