1.2 Supporting Evidence

Despite the high risk, very few YMSM are accessing HIV testing or care. According to a joint study conducted by the US CDC and the Thai Ministry of Public Health, only 50.3% of MSM in Thailand had ever been tested for HIV. Of those, merely 24.9% returned for their test results.⁴ As a result, only 12.5% actually knew their HIV status.⁵ Our previous research found that 73.3% of YMSM aged 15–19 and 45% of those aged 20–24 had never tested for HIV.⁶ This indicates that current HIV prevention efforts are failing to reach adolescents and young adults, especially in terms of HIV testing and linkage to care. Furthermore, many healthcare providers, including HIV test counselors, lack adequate knowledge of the Continuum of Prevention and Care (CPC), especially regarding the importance of achieving viral suppression, and often perpetuate stigma and discrimination against YMSM. These systemic issues further hinder engagement in HIV prevention and treatment services.

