2.4.1 Descriptive Analyses

Baseline demographic, behavioral, and health characteristics of participants will be summarized using descriptive statistics, stratified by study arm (intervention vs. control). Comparisons will be made between the two study sites (Ubon Ratchathani as the intervention site, and Mahasarakham as the control site) to assess initial differences and changes over time. Categorical variables will be presented as frequencies and percentages. Continuous variables will be summarized using means and standard deviations, or medians with interquartile ranges (25th to 75th percentile), depending on data distribution.

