2.4.2 Primary and Secondary Outcome Analyses

To evaluate the effects of the intervention over time, Generalized Estimating Equations (GEE) with appropriate link functions will be applied (e.g., logit for binary outcomes and identity for continuous outcomes). The models will include study arm, time (follow-up round), and their interaction to estimate the effect of the intervention across time points. Robust standard errors will be used to account for within-subject correlation due to repeated measurements. For incidence outcomes (e.g., HIV, chlamydia, and gonorrhea infections), person-time will be calculated, and incidence rate ratios (IRRs) with 95% confidence intervals will be reported.

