3.3 Primary Outcome

- **HIV testing uptake:**

Proportion of participants who report having ever tested for HIV during the 24-month follow-up period. Data will be collected from HIV testing records provided by the Ministry of Public Health national database.

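### The primary outcome is one cumulative yes/no per man, but SAP 6.2 gives it a covariate-free arm-by-time GEE and names no primary contrast; an adjusted month-24 comparison should be stated

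*Combined protocol and SAP*

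**What the plan says.** SAP 3.3 defines the primary outcome as "Proportion of participants who report having ever tested for HIV during the 24-month follow-up period", taken from national testing records. That is one value per man. How it would be coded at each visit, and whether tests before enrolment count, is not said.

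SAP 6.2 covers primary and secondary outcomes together, with a GEE (logit link for binary outcomes): "The models will include study arm (intervention vs. control), time (follow-up visits), and their interaction term to estimate intervention effects over time". Protocol 2.4.2 has the same model: "The models will include study arm, time (follow-up round), and their interaction to estimate the effect of the intervention across time points". Neither names a primary coefficient or time point, says whether baseline is a time level, or lists a covariate.

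Arm follows the place where a man lives, studies or works (protocol 2.2), with one city per arm (SAP 2). Protocol 2.4.1 compares the sites "to assess initial differences and changes over time", but only descriptively. Protocol 1.2 reports that "73.3% of YMSM aged 15–19 and 45% of those aged 20–24 had never tested for HIV", so prior testing varies strongly with age. SAP 3.1 words the testing objective for men never tested before; SAP 4.1 makes everyone with a baseline assessment the primary population.

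**The concern.** A cumulative outcome can only move from no to yes, and the question it answers is whether more men had tested by month 24. An arm-by-time model contains several candidate answers: the arm term, each interaction term, a joint test of the interactions, or a sum of terms. SAP 6.2 can be read as making the interaction the effect. For this outcome the interaction can describe something else, so a real difference could be missed, or a difference in timing alone could be reported as an effect.

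The second matter is bias. With two cities and no randomisation, men in one city may have tested more before the study began. If such men are analysed and the model has no covariates, that history can pass for an intervention effect.

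**Working it through.** The plan gives no effect size or power for 600 participants, so there is no figure of its own to reproduce. All testing rates below are assumed. Participants are treated as independent, city-level variation is left out, and tests are two-sided at 0.05. The results compare contrasts; they are not the trial's power.

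**Inputs from the documents.** 300 men per city. Protocol 1.2 gives never-tested shares of 45% and 73.3% by age, and 49.7% overall (100 − 50.3). These give 135, 149 and 220 never-tested men per city; everyone is 300.

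**1. What the interaction estimates.** With follow-up visits only and month 6 as reference, logit P(tested by t) = α + β·arm + γ(t) + δ(t)·arm, with δ(6) = 0. Then β = log OR(6) and δ(24) = log OR(24) − log OR(6). The month-24 effect is β + δ(24), not δ(24).

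**2. Precision.** Write q = 1 − p. Because status is cumulative, the covariance of month-6 and month-24 status is p6·q24. Summing over arms:
- Var(month-24 log OR) = Σ 1/(n·p24·q24)
- Var(interaction) = Σ [1/(p24·q24) + 1/(p6·q6) − 2/(q6·p24)]/n

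Example: 30% vs 50% at month 24 gives (4.762 + 4.000)/n. At n = 135 the SE is 0.255; log 2.333 = 0.847; z = 3.33; power = Φ(3.33 − 1.96) = 91%.

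**3. Rejection rates at n = 135 / 149 / 220 / 300 per city.**

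| Control vs intervention, month 6 then month 24 | Interaction | Month-24 contrast |
|---|---|---|
| Constant OR 2.33: 10% vs 20.6%, then 30% vs 50% | 5% at every n (its null is true) | 91 / 94 / 99 / 99.9% |
| Effect builds: 10% vs 13%, then 30% vs 50% | 35 / 38 / 52 / 65% | as above |

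If the gap widens from 8 to 12 points (10% vs 18%, then 30% vs 42%), the OR falls from 1.98 to 1.69 and the interaction is 0.86. Its estimate is below 1 in 70% (n = 149) to 78% (n = 300) of runs, and significantly below 1 in about 7% to 11%. The month-24 contrast favours the intervention in 58% to 86%.

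The opposite error also occurs. If the intervention city only tests earlier (35/45/50/50% vs 20/35/45/50% at months 6/12/18/24, 300 per city), the interaction rejects in over 99% of runs and the month-24 test in 5%.

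**4. Baseline as a time level, counting follow-up tests only.** Everyone is 0 at baseline, so the logit model separates. A trial fit gave an intercept of −28.5 and undefined robust SEs.

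**5. Prior testing, no true effect, 300 per city.** Assume 40% vs 50% previously tested, and that 60% of previously tested and 30% of never-tested men test in follow-up.
- Control: 0.40 × 0.60 + 0.60 × 0.30 = 42%
- Intervention: 0.50 × 0.60 + 0.50 × 0.30 = 45%
- Spurious difference 3.0 points (OR 1.13), SE √[(0.42 × 0.58 + 0.45 × 0.55)/300] = 0.040

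Simulated false positives: 12% unadjusted, 5% adjusted for prior testing. Using the age figures of protocol 1.2, and supposing only the two younger age groups were present, 0.267w + 0.55(1 − w) equals 0.40 at w = 0.53 and 0.50 at w = 0.18. The assumed imbalance would thus need 53% vs 18% aged 15–19. Men aged 25–29 are also eligible, so this only gives scale. If only never-tested men are analysed, this bias does not arise.

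**6. Lifetime reading, with baseline as a time level.** With 50.3% previously tested in both cities and 40% vs 55% new testing among the rest, the baseline-to-month-24 interaction has 68% power and an unadjusted month-24 comparison 55%. With the imbalance and rates of step 5 and no effect, lifetime proportions at month 24 are 58% vs 65% (OR 1.35). The unadjusted comparison then rejects in 42% of trials. The interaction is 1.35/1.50 = 0.90, SE 0.126, and rejects in about 14%.

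**The case against.** The strongest reply is that the model is not wrong; a contrast is merely unnamed. Protocol 2.4.2 speaks of the effect across time points, which fits visit-specific arm effects. Arm plus arm × month 24 is then the wanted contrast: in a test fit with 150 per arm it equalled the crude month-24 log OR (0.7433). Neither section sets month 6 as reference, and both design overviews list baseline as a time point. On a lifetime reading with baseline included, the interaction is a legitimate change-from-baseline contrast, and step 6 shows it can beat an unadjusted month-24 comparison. The separation in step 4 would be noticed at once.

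All of that stands, and it rules out three stronger conclusions that a reader might draw.

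- *The plan as written will miss the effect.* The 5% in step 3 belongs to one reading and one time pattern.
- *The plan will report harm.* The 70% to 78% counts the sign of an estimate; significant results below 1 are about 7% to 11%.
- *Visit-level status cannot be built because the registry holds only the latest test date.* Protocol 2.1.2 gives that date as an example, "including the date of the most recent HIV test, HIV status", not as a full list. SAP 3.3 refers to testing records, and SAP 3.4 uses the same database for "Proportion of HIV-positive participants who remain engaged in HIV care at months 6, 12, 18, and 24". The limit is not established.

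The reply does not supply the missing statement. A plan meant to fix the analysis in advance still leaves open which term is the primary result, and no reading of SAP 6.2 adds a covariate.

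**Conclusion.** The point holds in a limited form. The primary outcome is one cumulative yes/no per man, yet the plan gives it the model for repeated outcomes, names no primary contrast and adjusts for nothing in a comparison of two non-randomised cities.

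That the interaction equals OR(24)/OR(6) under the month-6-reference reading is an identity. What it costs (5% against 91% or more under a constant benefit) depends on assumed rates and on that reading being chosen. The prior-testing bias is separate: it needs previously tested men in the analysis and an imbalance between cities. The 12% against 5% rests on an assumed 10-point imbalance and assumed testing rates. Neither figure predicts what this trial will find.

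**What to change.** In SAP 6.2, and to match in protocol 2.4.2, state:

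> The primary effect is the between-arm risk difference at month 24 in the proportion of men with at least one HIV test recorded after enrolment and by their own month 24. It uses one record per participant with robust standard errors, adjusted for age group and, where previously tested men are included, for testing before enrolment. Tests before enrolment do not count.

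The month-24 arm contrast from the GEE (arm plus arm × month 24, time categorical) would serve equally if dated visit-level status is available, provided it is put on the risk-difference scale with the same adjustment.

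Reconcile SAP 3.1 (never-tested men) with SAP 4.1 (everyone), since this decides whether the prior-testing covariate is needed. Keep the arm-by-time GEE for condomless anal intercourse, PrEP use, retention in care and viral load, and keep person-time rate ratios for the incidence outcomes.

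The cost is SAP wording, covariates obtainable at enrolment, and test dates cut at each man's own month 24. That cut is needed because protocol 2.1.1 says: "Participant recruitment will be conducted over a one-year period". A single calendar cut-off would therefore give men unequal follow-up. Adjustment will not remove unmeasured differences between the two cities.
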